Clinical Performance Study Design:	Prospective, single blinded interventional randomised multicentre study
Sample size:	Up to 15,000 participants across the UK in the following stages: 
 • Pilot: target 800 participants • Study stage 1: up to an additional 5,600 participants • Study stage 2: up to an additional 8,600 participants There will be a data driven ‘stop-go’ decision at the end of each stage before progressing to the next stage.
Treatment/Intervention:	Participants will be blindly randomised into two arms; 
 • Intervention arm: Avantect test performed within prioritised time frame with intent to share only “detected” test results with the participants and their General Practitioners (GPs) in parallel to making a referral to the local secondary care clinical team for further investigations. All test results will be included in primary endpoint analysis. • Control arm (Standard of Care [SoC] arm): Participants will receive the current standard of care for diabetes management. Samples will be used for potential future Avantect testing and/or future research.
Number of specimens required per participant:	Three peripheral blood samples per participant (up to 30 mL in total) will be collected at three timepoints
Duration of the clinical performance study:	Participant involvement on trial: 3 visits over 12 months Length of remote follow-up collection for each participant: 36 months from consent Recruitment duration: 36 months Total study duration (including 12m analysis and report writing): 7 years

URL for Database:	https://www.imedidata.com
URL for randomisation:	https://www.imedidata.com

Primary Study Endpoints:	Pilot: Recruitment rate Study stage 1 & 2: Sensitivity and specificity of Avantect test for detecting pancreatic cancer, pancreatic cancer resectability rate
---------------------------------	--

Secondary Study Endpoints:	Secondary endpoints (pilot and study stage 1 and 2 combined) will include pancreatic cancer stage shift, PPV, NPV and proportion of pancreatic cancer patients undergoing surgical resection
Exploratory Endpoints	Overall survival (time-to-event) Time to pancreatic cancer diagnosis (NOD to pancreatic cancer diagnosis) 6-item Spielberger State Trait Anxiety Inventory (STAI) Performance characteristics for high-grade neoplasia
Total Number of Sites:	Up to 3,000 GP practices and up to 200 Specialist Diabetes Service Centres

TRIAL SCHEMA

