5. SELECTION AND ENROLMENT OF PARTICIPANTS

5.1 PARTICIPANT ENROLMENT

Participants will be approached to take part in SAFE-D via their GP or SDSC. Electronic Health Record (EHR) searches will be undertaken by the study team at participating GP practices and subjects with a recent diagnosis of DM (within six months) will be eligible for enrolment. Subjects attending SDSCs will also be eligible for enrolment. In addition, participants may self-refer for the study via the SAFE-D booking website. Participants who sign the consent form will be considered enrolled.

The study is expected to enrol 15,000 participants over 36 months, including a six-month pilot study to evaluate recruitment feasibility and to estimate the number of participating sites required, and an interim analysis for futility and efficacy (Stage 1). Participants will remain in the study for 12 months, attending study visits at enrolment (baseline (T0)) and at six (T1) and 12 months (T2) post enrolment. There may be planned recruitment stops between the Pilot and Stage 1 of the study to allow for a data driven 'stop-go' decision should this decision not be concluded in the lead up to Stage 1. Recruitment will continue once the Stage 1 interim analysis requirements have been met and will continue unless that analysis concludes that the intervention is futile. Total study duration is expected to be 7 years including 12 months for analysis and report writing.

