7.6.4 Timepoint T3 (2 years after T2)

T3 refers to the three years of follow-up (following recruitment at T0) which will be collected via linkage with the cancer and mortality registry. At the time of writing the cancer registry is managed by the National Cancer Registration and Analysis Service which sits within NHS England, and the mortality register is managed by the Office for National Statistics but can be accessed through NHS England. Cancer and mortality registry data will still be required and sought even if the owner of the dataset changes in the future. A cancer and mortality registry download will be obtained on three

occasions: once 6,400 participants have been recruited, once 15,000 participants have been recruited, and at 3 years post last participant recruited.

Data Collection from Cancer Registry:

- Any cancer diagnosis (ICD10 C00-D48)
- Date of cancer diagnosis
- Site of cancer diagnosis
- Stage of cancer at diagnosis
- Histology of cancer
- Survival status
- Cancer treatments

Data Collection from Mortality Registry:

[figure not shown]
- Date of death
- Causes of death

The local site study team will collect and keep NHS number, address and contact details (including 1 or 2 phone numbers and an email address) from all participants. NHS numbers and dates of birth for all participants will be shared securely by site to the SCTU. SCTU will then pass on the NHS numbers and dates of birth to the administrators at the registries to allow them to perform registry searches on three occasions during the study. The local site team will also share with the SCTU study team, via secure email, the contact details (name, postal and email address) for a select number of participants (numbers to be defined) who have consented to optional further research questionnaire.

Addresses will be used by sites to contact participants with any Avantect “Detected” results by post. Phone numbers will be used by sites to contact participants if required throughout the study, including contacting participants to inform them of a “Detected” Avantect test if deemed more appropriate than by post alone (at the discretion of the clinical team).

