7.9.2 Abnormal imaging outcome

Participants referred for imaging who have abnormal imaging results will be returned to routine clinical care (via local HPB team) for further clinical management as per current NHS practice.

If pancreatic cancer, other solid pancreatic lesion or other cancer type is identified based on imaging and biopsy is performed then de-identified imaging reports and any subsequent de-identified biopsy or resection pathology reports will be collected as part of the study clinical data. Participant would discontinue further study blood collections. Diagnoses will be based on reports of pathologic evaluation performed at the treating institute. Digital Imaging and Communication in Medicine

(DICOM) images will be obtained and reviewed at the end of the study phase as a quality control measure. If cyst fluid is sampled the de-identified cytology and any cyst fluid chemistry lab reports will be obtained and included in study data.

If imaging is abnormal and no biopsy or surgery is planned, de-identified imaging reports will be provided as part of study data and the cancer and mortality registry searches will be completed as planned. Participants with abnormal imaging results (suggestive of cancer) will discontinue further blood collection, but cancer and mortality registry searches will be completed as planned.

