9.3 STUDY TIMEPOINTS

There will be three timepoints for blood collection: at baseline (T0), 6 months +/- 2 weeks post-baseline (T1), and 12 months +/- 2 weeks from baseline (T2). For each study timepoint, the Avantect test will be conducted. For samples collected from participants assigned to the intervention arm, the Avantect test will be assessed as soon as possible within 14 business days of receipt of samples in the analysing laboratory at ClearNote Health. Those with positive test results (test result = Avantect “detected”) in the intervention arm will undergo diagnostic pancreas imaging. Samples collected from participants assigned to the Control arm will be stored for potential future Avantect testing or future research.

The study design comprises a pilot and two study stages:

- Stage 1 Analysis will be carried out 6 months after the T1 visit for 3,200 participants in the intervention arm. Only participants followed up for a minimum of 6 months after the T1 visit in the intervention arm will be included in this analysis.
- Stage 2 Analysis will be carried out after 3-year follow-up data has been collected for all 15,000 participants.

In addition, during the study annual readouts will be provided to the data monitoring committee to monitor study progress and inform on decisions to continue or stop the study.

The diagnostic performance of the Avantect test results will be summarised according to the pancreatic cancer diagnoses collected by the point of analysis. The stage shift, and resection rate of pancreatic cancer will be summarised by arm. For this purpose, a positive test at any timepoint will be considered a ‘positive prediction’ e.g., if a participant has a negative result at T0, but a positive result at T1, their overall prediction will be considered as at-risk of pancreatic cancer.

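### The last registry download falls on the day the last recruit reaches 36 months, so any registration delay loses late cancers and biases sensitivity and NPV modestly upward

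*Protocol*

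**What the plan says.** Protocol 7.6.4 (Timepoint T3) obtains three-year outcomes by linkage to the cancer and mortality registries. The first download is at 6,400 recruits; the other two are "once 15,000 participants have been recruited, and at 3 years post last participant recruited". Identifiers go to the registries "to allow them to perform registry searches on three occasions during the study", and no later search is planned. The cancer registry supplies diagnosis, date, stage, histology and treatment. The mortality registry supplies date and causes of death.

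The synopsis gives "Recruitment duration: 36 months", "Length of remote follow-up collection for each participant: 36 months from consent" and "Total study duration (including 12m analysis and report writing): 7 years". Section 5.1 repeats the total: "Total study duration is expected to be 7 years including 12 months for analysis and report writing".

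Section 9.3 sets the condition for the final analysis: "Stage 2 Analysis will be carried out after 3-year follow-up data has been collected for all 15,000 participants".

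Cancers found after a 'detected' result have a second route into the data. Section 7.9.2 says that imaging reports and "any subsequent de-identified biopsy or resection pathology reports will be collected as part of the study clinical data". Under 7.8.2, participants with a 'not detected' result are not told and simply continue their visits. Control participants have no study imaging.

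**The concern.** The third download can hold complete 36-month data for the last recruits only if the registry records a cancer, its stage and its treatment without delay. With a delay of L months, a diagnosis made in the last L months before the download is not yet there. This affects only people recruited in the last L months of accrual, and only the end of their follow-up.

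The loss is not neutral for test accuracy. A cancer found by acting on a 'detected' result at T0, T1 or T2 comes in from site reports and, being early, has had ample time to be registered. A cancer the test missed surfaces later through usual care, and the study learns of it mainly from the registries. Losing such a case removes a false negative, which raises sensitivity (a pass/fail co-primary) and NPV.

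The between-arm endpoints are exposed in another way. Late control-arm cancers may be absent, or present without stage or treatment. Resection also follows diagnosis, so a cancer diagnosed just before the download cannot yet show its resection, even if registration itself were immediate.

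**Working it through.** **Timeline.** 36 (accrual) + 36 (follow-up) + 12 (analysis) = 84 months = 7 years. The last recruit, at month 36, reaches 36 months of follow-up at month 72, which is the date of the third download. There is no slack between the two.

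**The plan's own figures (9.2).** 7,500 × 0.975 = 7,312 per protocol; × 1% = 73 cancers; × 65% = 47.5, entered as 48 detected; 73 − 48 = 25 missed. Sensitivity is 48/73 = 65.8%. These reproduce.

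**Accrual (2.1, 5.1).** The plan has 800 in the six-month pilot and 15,000 over 36 months. Assuming level recruitment after the pilot, 14,200/30 = 473 per month, so each late month holds 14,200/(15,000 × 30) = 3.156% of participants.

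**Share of cancers lost.** A person recruited s months before the end of accrual (s < L) loses the last L − s months of follow-up. Summed over the last L months this gives L²/2. Let d be the share of cancers diagnosed per month of late follow-up. Then

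f = 0.03156 × (L²/2) × d, with L²/2 = 18, 72 and 162 for L = 6, 12 and 18.

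The protocol gives no delay, so the three values of L are assumptions. Four assumed timings set d:

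- 60/20/20% by year: d = 0.20/12 = 1/60
- even over 36 months: d = 1/36
- all in months 12–36: d = 1/24
- 10% after month 18, spread evenly: d = 0.10/18 = 1/180

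**Sensitivity.** The 48 detected cancers are taken as fully captured and the loss is applied to the 25 missed: sensitivity = 48/(48 + 25(1 − f)). For example, with L = 12 and even timing, f = 0.03156 × 72/36 = 6.31%. Missed cancers lost = 25 × 0.0631 = 1.58, and 48/71.42 = 67.2%.

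| Timing of diagnoses | L = 6: f; lost of 25; sensitivity | L = 12 | L = 18 |
|---|---|---|---|
| 60/20/20% by year | 0.9%; 0.24; 66.0% | 3.8%; 0.95; 66.6% | 8.5%; 2.13; 67.7% |
| Even over 36 months | 1.6%; 0.39; 66.1% | 6.3%; 1.58; 67.2% | 14.2%; 3.55; 69.1% |
| All in months 12–36 | 2.4%; 0.59; 66.3% | 9.5%; 2.37; 68.0% | 21.3%; 5.3; 70.9% |
| 10% after month 18 | 0.3%; 0.08; 65.8% | 1.3%; 0.32; 66.0% | 2.8%; 0.71; 66.4% |

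If every cancer is diagnosed within 18 months of T0, nothing is lost for L up to 18, because the truncated window starts no earlier than month 36 − 18 = 18.

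**NPV.** The planned value is 6,877/6,902 = 99.64%. In the most extreme cell above, 5.3 false negatives are counted as true negatives: 6,882.3/6,902 = 99.71%. The direction is the same and the size is negligible.

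**Effect on the sensitivity decision.** Suppose true sensitivity equals the 49% null in 9.4, with 73 cancers: 35.8 detected and 37.2 missed. After loss, n′ = 35.8 + 37.2(1 − f) and p′ = 35.8/n′. Success needs an estimate above 0.49 + 1.881√(0.49 × 0.51/n′). By normal approximation, the false-success rate rises from 3% to 3.3–3.8% (L = 6), 4.3–7.1% (L = 12) and 6.6–17.8% (L = 18) over the first three timings.

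**Control arm.** With even timing, 73 × f = 1.2, 4.6 or 10.4 control-arm cancers are not yet recorded. Under a simpler model of level accrual over all 36 months, control-arm cancers fall from 73 to 72.0, 68.9 or 63.9. Resectability power at one-sided 0.03 then goes from 95.9% to 95.7%, 95.2% or 94.2%.

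**The case against.** The strongest reply has four parts.

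- **The delay is assumed.** No section states one, and at L = 0 no diagnosis is lost. This stands. The figures are a range over assumptions and not an estimate. What needs no assumption is that the schedule has no margin.
- **The protocol's own premise on timing.** Section 4 says that most cancers by far are diagnosed within 12–18 months of the diabetes diagnosis, and T0 falls up to about 6 months after that diagnosis. Every lost cancer falls after month 18 from T0. This stands too and makes the last row of the table the closest to the plan. But section 4 does not say all, 9.2 counts events over three years, and cancers missed by tests up to month 12 may come later than average.
- **Section 9.3 already requires complete data,** 2.5 ends the study only when follow-up data are collected and cleaned, and 5.1 calls 7 years an expectation. A sponsor could rely on 9.3 and wait. But 7.6.4 allows three searches and dates the last, so the two sections agree only if the delay is zero.
- **Other sources dilute the asymmetry.** The mortality registry also gives causes of death, so a fatal missed cancer may be found there. Some participants with a 'detected' result depend on the registry as well: those who decline imaging (7.8.1) and those with normal imaging who are diagnosed later (7.9.1). This stands and reduces the bias.

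A reader might infer three stronger things that the document does not support. First, that lost control-arm cancers inflate sensitivity: they cannot, since sections 2.2 and 9.4 define sensitivity in the intervention arm only. Second, that sensitivity could read as high as 76.7%. That figure takes the 14.2% loss on all 73 cancers and counts every lost case as missed. With even timing about 36 of 73 cancers fall after month 18, yet only 25 are missed in all, so at least 11 late ones had a 'detected' result. Third, that the 38% of participants recruited in the last 12 months represents the loss: the share of cancers lost at L = 12 is 1.3–9.5%.

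**Conclusion.** The point holds, at modest size. Section 7.6.4 does not secure the complete three-year data that 9.3 requires, and the timeline leaves no room to obtain them before the analysis period. The resulting bias in sensitivity and NPV runs towards success.

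For sensitivity it is minor at an assumed 6-month delay (at most +0.5 points), +0.9 to +2.2 points at 12 months and +2.0 to +5.2 points at 18 months. It is at most +0.6 points if only 10% of cancers fall after month 18. These sizes rest on level accrual after the pilot, full capture of the 48 detected cancers and reliance of the 25 missed ones on the cancer registry. Because the last two are not strictly true, the real effect would be smaller under each timing.

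For the between-arm comparisons the issue is missing late cases and missing stage or resection data. The loss of resectability power is slight.

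**What to change.** Either of two changes would do.

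1. In 7.6.4, take the third download when the registry confirms that registration, stage and treatment are complete through the last participant's 36-month date. The cost is a final readout later by the registry delay, part of which may fit within the 12 months set aside for analysis; otherwise the 7-year total needs adjusting.
2. Keep the download date and state in 9.3 and 9.4 that the registry's complete-through date is a single diagnosis cut-off for all cancers in both arms, including those already known from site reports. State the shorter follow-up of the last recruits, and reword the 9.3 condition to match. The cost is a few months less follow-up for those recruits.

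Each is a sentence or two of text. The choice should be fixed before outcomes are known, so that the cut-off cannot be picked afterwards.

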7.8 AVANTECT OUTCOMES AND FOLLOW UP FOR PARTICIPANTS IN THE INTERVENTIONAL ARM

7.8.1. Detected

The CI will request the SAFE-D site team to notify participants in the intervention arm with Avantect “detected” test results and their GPs of the result via letter and an optional phone call (at the discretion of the clinical study team). The CI will also request the site team to arrange an urgent suspected cancer referral (tumour specific pathway referral) to local hepatobiliary (HPB) service Local Collaborator for a pancreas MRI (or CT if MRI is contraindicated) and imaging will be scheduled as per standard of care for suspected cancer pathway.

If participant with Avantect “detected” test result is unable or unwilling to undergo imaging of pancreas, participant will be removed from further Avantect testing, but will be included in the analysis and any cancer and mortality registry searches.

7.8.2. Not detected

Participants in the intervention arm who have an Avantect “not detected” test result will not be informed of their result and will continue with study schedule of observations and procedures.

7.8.3. Quantity Not Sufficient (QNS)

In the event of a sample without adequate cfDNA concentration, a pancreatic cancer classification cannot be provided and a QNS report will be generated. The participant will be invited to provide a repeat blood sample within the predefined study timepoints (see Section 6.1).

7.9 IMAGING RESULTS

7.9.1 Normal imaging outcome

If imaging did not show signs of pancreatic cancer or pancreatic cystic lesion with high grade dysplasia and/or neoplasia then the participant will continue with the remaining study visits.

7.9.2 Abnormal imaging outcome

Participants referred for imaging who have abnormal imaging results will be returned to routine clinical care (via local HPB team) for further clinical management as per current NHS practice.

If pancreatic cancer, other solid pancreatic lesion or other cancer type is identified based on imaging and biopsy is performed then de-identified imaging reports and any subsequent de-identified biopsy or resection pathology reports will be collected as part of the study clinical data. Participant would discontinue further study blood collections. Diagnoses will be based on reports of pathologic evaluation performed at the treating institute. Digital Imaging and Communication in Medicine

(DICOM) images will be obtained and reviewed at the end of the study phase as a quality control measure. If cyst fluid is sampled the de-identified cytology and any cyst fluid chemistry lab reports will be obtained and included in study data.

If imaging is abnormal and no biopsy or surgery is planned, de-identified imaging reports will be provided as part of study data and the cancer and mortality registry searches will be completed as planned. Participants with abnormal imaging results (suggestive of cancer) will discontinue further blood collection, but cancer and mortality registry searches will be completed as planned.

7.9.3 Abnormal imaging outcome showing pancreatic cystic lesion

For abnormal imaging outcomes showing a pancreatic cystic lesion, European or local guidelines will be followed.

IPMN or Mucinous cystic neoplasms (MCN) that, after surgical and histopathological evaluation, show a high-grade dysplasia phenotype will be considered as pancreatic cancer¹². Otherwise, low grade dysplasia and other non-mucinous cystic lesions will not be considered as pancreatic cancer.

Participants in the intervention arm with Avantect “detected” test results and for whom pancreatic cysts have been found by MRI/CT, and surveillance has been recommended, will continue study visits as scheduled and will be considered as non pancreatic cancer outcome regardless of the size of the cyst until proven otherwise by pathological examination (Appendix III)

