 - Sensitivity of Avantect test for detecting PC – number of individuals in the intervention arm with one or more Avantect “detected” test results and PC divided by the number of individuals in the intervention arm with PC.
 - Specificity of Avantect test for ruling out PC – number of individuals in the intervention arm with no Avantect “detected” test results, at least one Avantect “not detected” test result and no diagnosis of PC divided by the number of individuals in the intervention arm with no diagnosis of PC.
 - Resectability rate – number of individuals with PC deemed resectable by the study multidisciplinary team (MDT) divided by the number of PCs.

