2.4 TABLE OF ENDPOINTS/OUTCOMES PILOT

	Objective	Outcome Measures	Summary method(s)
Primary	To determine the recruitment rate	Recruitment rate	
 Percentage recruited of all participants invited Number of individuals recruited per month

STUDY STAGE 1 and 2 (analysis inclusive of pilot):

	Objective	Outcome Measures	Summary method(s)
Primary	To estimate the proportion of PCs deemed resectable	Resectability rate	Percentage of PCs deemed resectable by the study MDT [compared between arms]
	To estimate the sensitivity of the Avantect test in detecting PC	Sensitivity	Percentage with PC diagnosed who have an Avantect “detected” result [within intervention arm]
	To estimate the specificity of the Avantect test in ruling out PC	Specificity	Percentage without PC diagnosed who have one or more Avantect “not detected” results and no Avantect “detected” results [within intervention arm]
Secondary	To determine the effect of the Avantect test on PC stage shift	Stage shift	Percentage of PCs diagnosed at stage I/II [compared between arms]
	To estimate the PPV of Avantect for detecting PC	PPV	Percentage with an Avantect “detected” result who have PC diagnosed [within intervention arm]

	To estimate the NPV of Avantect for ruling out PC	NPV	Percentage of individuals with no Avantect “detected” test results who have no diagnosis of PC [within intervention arm]
	To estimate the proportion of PCs that are resected	Resection	Percentage with PC who underwent resection [compared between arms]
Exploratory	To estimate the time from NOD diagnosis to PC diagnosis	Time to diagnosis	Kaplan-Meier curve Hazard ratio [within intervention arm]
	To estimate the overall survival of study participants	Overall Survival	Kaplan-Meier curve Hazard ratio [compared between arms]
	Assess the effect of the Avantect test on state anxiety over time	6-item STAI	T-test or non-parametric alternative if suitable [compared between arms]
	To investigate the performance characteristics for high-grade neoplasia	Sensitivity Specificity PPV NPV	As described above, but disease positive is defined as PC and/or high-grade mucinous cysts and non-cases defined as no pancreatic cancer or high-grade mucinous cysts. This will be repeated where high-grade mucinous cysts are considered as disease positive and PCs are excluded. [within intervention arm]

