7.10 DEFINITION OF BIOPSY OUTCOMES

The categories of clinical diagnostic follow-up findings are defined as follows:

- Histologic findings show pancreatic cancer, any stage (I-IV) based on American Joint Committee on Cancer (AJCC) v8.0.
- Histologic findings are indeterminate
- Histologic findings are consistent with pre-neoplastic lesions (IPMNs, mucinous cystadenoma or with pancreatic intraepithelial neoplasia (PanINs)).
- Histologic findings are consistent with an inflammatory process (benign disease)

Overall, the reference method will be histopathologic confirmation of PC, and/or definitive imaging diagnosis of PC.

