Resection rate of PC. The analysis will be conducted by comparing resection between the intervention and control arms. With a sample size of 15,000, PC prevalence of 1%, and 2.5% lost to follow-up, there will be an expected 73 cases of PC in each arm. It is assumed that 5% of those deemed resectable will not undergo resection, for an expected rate of 38% (28/73) in the Intervention arm versus 13% (9/73) in the control arm. Resection rate will be considered successful if the proportion in the intervention arm is higher than the rate in the control arm at a one-sided p-value of 0.05.

For analyses of exploratory outcomes, the following applies:

Time-to-event outcomes (time to PC diagnosis and overall survival) will be analysed using a Cox regression model to determine the hazard ratio (and 95% confidence interval) between groups. This will be supported by a Kaplan-Meier plot for each group, median survival (and 95% confidence intervals), and estimates of 3-year survival (T0-T3) (alongside the difference in proportions and corresponding 95% confidence interval). The 6-item STAI will be analysed using a t-test or non-parametric suitable alternative if data are not normally distributed. Performance characteristics for high-grade neoplasia include sensitivity, specificity, PPV and NPV. They will be analysed as described

SAFE-D Clinical Performance Study Protocol Version 4, IRAS Ref: 326332 31-JUL-2025 Page 49 of 68

above, when high-grade neoplasia is also considered as Disease Positive, and when high-grade neoplasia alone (with the exclusion of pancreatic cancer) is considered as Disease Positive. Two-sided p-values will be presented for exploratory outcomes.

Unless otherwise stated, continuous data will be presented as means and standard deviations and analysed using a linear regression modelling framework. If data are skewed, medians and ranges will be presented. To analyse skewed data we will attempt to find a suitable transformation to allow a linear modelling approach. If this is not possible, we will explore whether another suitable parametric distribution fits the data. If not, a non-parametric approach, such as quantile regression, will be used. Binary data will be reported in terms of odds ratios and analysed using logistic regression modelling, unless otherwise stated.

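### Surgically proven high-grade dysplasia counts as pancreatic cancer in 7.9.3 but as a separate category in 2.4 and 9.4; counting it favours the test, by an amount the protocol does not allow one to fix

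*Protocol*

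**What the plan says.** **The case rule.** Protocol 7.9.3: "IPMN or Mucinous cystic neoplasms (MCN) that, after surgical and histopathological evaluation, show a high-grade dysplasia phenotype will be considered as pancreatic cancer". The same section leaves low-grade and non-mucinous cysts out of PC, and treats cysts under surveillance as non-PC until pathology shows otherwise.

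**High-grade lesions as a separate category.** The exploratory row of the table in 2.4 first widens the case set: "disease positive is defined as PC and/or high-grade mucinous cysts and non-cases defined as no pancreatic cancer or high-grade mucinous cysts". It then continues: "This will be repeated where high-grade mucinous cysts are considered as disease positive and PCs are excluded". Section 9.4 repeats the second analysis: "when high-grade neoplasia alone (with the exclusion of pancreatic cancer) is considered as Disease Positive". Section 7.10 has a histology category apart from stage I–IV cancer: "Histologic findings are consistent with pre-neoplastic lesions (IPMNs, mucinous cystadenoma or with pancreatic intraepithelial neoplasia (PanINs". That category is not split by grade.

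**Where PC enters the co-primaries.** Sensitivity and specificity (2.2, 9.4) are defined by PC diagnosis. Resectability in 2.2 is the "number of individuals with PC deemed resectable by the study multidisciplinary team (MDT) divided by the number of PCs". Neither section says whether a resected high-grade cyst is a PC.

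**Who is imaged.** By 9.3, participants with a positive test "in the intervention arm will undergo diagnostic pancreas imaging". For controls the synopsis says: "Participants will receive the current standard of care for diabetes management". Section 7.6.4 plans registry linkage for codes C00–D48 in all participants.

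**The concern.** PC defines the case set for all three co-primaries and for every secondary endpoint, so two incompatible rules leave the main results open to choice.

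The rule in 7.9.3 is also not neutral between arms. Surgery is a condition of being counted, so a counted lesion adds one to the denominator of resectability and almost always one to its numerator; the same holds for the resection rate. Study-triggered pancreas imaging follows a *detected* result in the intervention arm, and section 1.2 itself expects the test to pick up some neoplastic cysts. Most such cases should therefore arise in that arm and carry a positive test, which raises sensitivity as well. A favourable result could come partly from extra pre-invasive lesions, with no invasive cancer found at a more resectable stage.

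The exploratory analyses suffer too. If surgically proven lesions are already PC, the combined analysis gains nothing from them, and the analysis without PCs loses them.

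**Working it through.** **Inputs from the protocol.** 73 PCs per arm; resectability 14% (usual care) versus 40%; 2.5% loss; 1% event rate (all 9.2). Final success rule at one-sided p 0.03 (9.4). Stage 1 futility line for resectability 21.0%, and 3,200 intervention participants (9.2). Expected confusion matrix 48 / 25 / 362 / 6,877 (9.2).

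**Assumed, because the protocol gives no figure.** The number of surgically proven high-grade lesions counted as PC: k in the intervention arm and j in control, each treated as resectable.

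**Step 1: the plan's own figure.** Exact enumeration of the pooled one-sided z-test at 0.03, 73 per arm, 40% versus 14%, gives 96.2% power (95.9% by the normal formula). The plan states 96.5%, so this is close. Also 73/0.975 = 74.9, rounded up to 75, and 75/0.01 = 7,500 per arm, as stated.

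**Step 2: resectability when there is no true effect.** Intervention resectable count: Bin(73, 0.14) + k out of 73 + k. Control: Bin(73, 0.14) + j out of 73 + j. The expected intervention rate is (73 × 0.14 + k)/(73 + k). For k = 5 this is 15.22/78 = 19.5%. Summing the exact probabilities of all tables that pass the test at one-sided 0.03:

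| Lesions, intervention vs control | Expected rates | False-positive rate, this endpoint |
|---|---|---|
| 0 vs 0 | 14.0% vs 14.0% | 3.0% |
| 1 vs 0 | 15.2% vs 14.0% | 4.4% |
| 2 vs 0 | 16.3% vs 14.0% | 6.1% |
| 3 vs 0 | 17.4% vs 14.0% | 8.3% |
| 5 vs 0 | 19.5% vs 14.0% | 14.5% |
| 5 vs 1 | 19.5% vs 15.2% | 9.9% |
| 5 vs 2 | 19.5% vs 16.3% | 6.1% |
| 5 vs 5 | 19.5% vs 19.5% | 1.3% |

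The inflation comes from the imbalance between arms; equal numbers do not produce it. Section 9.4 also gives a 98.5% one-sided interval for the final analysis. At one-sided 0.015, 5 vs 0 gives 8.5%, against 1.5% with none.

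**Step 3: stage 1.** Resectability is then judged within the intervention arm, so control lesions cannot offset anything. Assume 32 PCs (1% of 3,200; the 1% is a 3-year figure, so fewer is plausible) and true resectability of 14%. Three added lesions give (32 × 0.14 + 3)/(32 + 3) = 7.48/35 = 21.4%, just above the 21.0% futility line.

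**Step 4: sensitivity and resection.** If five added lesions all carry a positive test, the planned 48/73 = 65.8% becomes 53/78 = 67.9%. A true sensitivity equal to the 49% null in 9.4 reads as (73 × 0.49 + 5)/78 = 52.3%. The planned resection rate of 28/73 = 38.4% becomes 33/78 = 42.3%.

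**The case against.** **The number of lesions is not documented.** Section 1.2 says only that the test may detect some neoplastic cysts. Of about 410 expected *detected* participants, 362 have no PC. Five resected high-grade lesions would be 5/362 = 1.4% of these, and ten would be 2.8%, while 7.9.3 names surveillance as one outcome for cysts. This stands: the size is unknown, and the larger counts have no support in the text.

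**Controls can contribute.** The rule is not worded for one arm, and registry linkage covers both, so a lesion resected in usual care could count. This stands; it is why the 5 vs 1 and 5 vs 2 rows are shown and why the claim is *mainly* the intervention arm.

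**Stronger readings that the documents do not support.**
- A reader might take 14.5% as the trial's false-positive rate. Section 9.2 requires all three co-primaries to succeed, so it applies to one endpoint.
- A reader might infer that such lesions are always resectable. Section 7.9.4 rests the endpoint on study review of scans, not on whether surgery took place; almost always is as far as one can go.
- A reader might infer that only true positives are added. A participant with no *detected* result whose lesion is resected in usual care and reaches the registry would be a false negative.
- A reader might infer that the exploratory analyses are empty or duplicates. Sections 2.4 and 9.4 do not require surgical proof, and 7.9.2 collects cyst cytology, so lesions not proven by surgery could remain. The text does not say that this is the intention.

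**Counting precursors may be deliberate.** Section 1.2 explains why finding them matters. That could justify an endpoint that includes them, but not two definitions in one protocol.

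**Conclusion.** The contradiction is explicit, and no section resolves it. Because PC is the case definition for every co-primary, this is a rule that conflicts with itself, not a detail that can wait for the statistical analysis plan.

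The direction of the bias follows from the design: surgery is a condition of counting, and study imaging follows a *detected* result in one arm. The size does not follow from the documents. For 1 to 5 lesions in the intervention arm and none in control, the false-positive rate for resectability runs from 4.4% to 14.5% against 3.0%. One or two control lesions bring the upper figure down to 9.9% or 6.1%, and the stricter 0.015 level brings it to 8.5%. These figures assume 73 invasive cancers per arm, 14% truly resectable in both, every added lesion judged resectable, and a pooled z-test in place of the logistic model named in 9.4.

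**What to change.** Before the stage 1 analysis, state one case definition and use it in 2.2, 2.4, 7.9.3, 7.10 and 9.4:

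- For all primary and secondary endpoints, PC excludes high-grade dysplasia without invasive cancer.
- PC and/or high-grade neoplasia remains the exploratory endpoint it already is. State whether the analysis without PCs includes lesions not proven by surgery.
- Split the pre-neoplastic category in 7.10 by grade, and apply the same histology rule to registry cases in both arms.
- Report resected high-grade lesions by arm, with a sensitivity analysis that counts them as PC.

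With these lesions excluded, the calculation returns to a 3.0% false-positive rate and 96.2% power at 40% versus 14%. The cost is slightly fewer cases and edits to several sections. Left until after stage 1, the choice would be made with data in hand. The change concerns the endpoint definition only, not how any lesion is managed.
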